5.2 EXCLUSION CRITERIA

Practices, providers and parent/caregivers may be excluded at the discretion of the PI. Our plan is to exclude practices that are solo-practitioners and that have paper records. If we have difficulty recruiting, we may include these practices.

5.3 LIFESTYLE CONSIDERATIONS

N/A

5.4 SCREEN FAILURES

N/A

5.5 STRATEGIES FOR RECRUITMENT AND RETENTION

Practices: We will invite all potentially eligible practices that are affiliated with WU PAARC and Community Outpatient Practice Experience (COPE) to participate. The first 20 practices that agree to participate will be randomly assigned to the intervention or control group using an allocation ratio 1:1.

Practices may be contacted by email, fax, letter, phone, or in-person to invite participation. All providers in the practice will be invited to participate. [name] and/ or a member of the study team will meet with those who are interested in learning more about the study to explain the details of study participation and answer any questions. These meetings will be held at the provider's office. If we experience difficulty with recruitment, we may expand our criteria to include solo practitioners and practices who still maintain paper records, as well as practices in the community that are not affiliated with WU PAARC or COPE.

We anticipate that we will recruit ~80 primary care pediatricians from the 20 participating practices. We estimate the racial/ethnic breakdown of participating physicians based on surveys completed by members of our PBRN, the available study population. We estimate that 27% of participating physicians will be male, ~84% will be Caucasian, 6% African American, 7% Asian. About 6% will be Hispanic. Due to the 2020 Coronavirus pandemic, the baseline parent survey was eliminated. Changes in EMR protocols has made parent contact information inaccessible, therefore the electronic parent survey has been completely eliminated from the study. The goal of this survey, to assess if parental satisfaction with HPV vaccine care differed between study groups, will be met by adding questions to the provider survey. Specifically, to assess provider experiences with patient complaints and loss to the practice related to HPV vaccine delivery, repeating the measure from the baseline provider survey.

Incentives: We will provide financial compensation for time taken to participate in the study including \$500/year for the business entity of each participating practice for administrative expenses (obtaining the lists of eligible patients, allowing study team access to medical records, etc.). We will also provide \$50 for providers who complete study surveys.

We will provide opportunity for all participating pediatricians to earn American Board of Pediatrics (ABP) Maintenance of Certification (MOC) Part-4 credit to maintain board certification in general pediatrics. To accomplish this, pediatricians must be up to date in four areas including professional standing (part 1), lifelong learning (part 2), cognitive expertise (part 3) and improving professional practice (part 4). Every 5 years, each pediatrician is required to earn 100 points through part 2 and part 4 activities, with 40-60 points for each part. Part 4 activities require pediatricians to demonstrate competence in systematic measurement and improvement in patient care work that is intended to improve child health. Our

project is approved by the American Board of Pediatrics and is sponsored by Saint Louis Children's Hospital, Washington University School of Medicine, and meets requirements for part 4 activities. To earn MOC-credit, the pediatrician must participate in the intervention for at least 12-months.

We will consult with our 6-member Advisory Board of key stakeholders (pediatricians, pediatric nurse practitioners and parents) to receive their advice about strategies to increase recruitment and retention of practices.

6 STUDY INTERVENTION(S) OR EXPERIMENTAL MANIPULATION(S)

6.1 STUDY INTERVENTION(S) OR EXPERIMENTAL MANIPULATION(S) ADMINISTRATION

6.1.1 STUDY INTERVENTION OR EXPERIMENTAL MANIPULATION DESCRIPTION

The intervention occurs at the level of the practice.

All providers (intervention and control groups) will receive information provided by the CDC to assist providers to improve use of HPV vaccine including the current recommendations, background information about the vaccine, and patient educational materials. The CDC website will be distributed. Baseline HPV vaccination rates will also be given to all providers.

The intervention:

The theory-based, multicomponent intervention includes: 1) an educational video to increase the provider's knowledge about guideline recommendations and patient and practice benefits of vaccination by age 13; 2) audit and feedback of vaccine coverage to increase motivation to engage in practice change; 3) a communication strategy to improve the provider's communication skills and their self-efficacy to address parental hesitation; and 4) practice facilitation to support practice change to develop a sustainable HPV vaccine delivery system. The intervention is based on CDC guidelines, addresses specific barriers to HPV vaccine use in primary care practices, and has multiple components. It is informed by the Theoretical Domain Framework, a behavioral change theory specific for primary care providers, and has been refined by pilot testing. We anticipate that the intervention will increase on-time HPV vaccination by increasing providers' capability (communication skills) and their motivation (confidence in their capabilities) to deliver on-time HPV vaccination.

The intervention is designed for sustainability, using practice facilitation to support lasting practice change. It will be delivered through a series of brief practice visits with the facilitator that occur every 1-4 weeks over 2 years. The usual care control group will be offered the intervention after the evaluative study is completed. Visits will be completed either in-person or through zoom video conferencing if face-face visits are not possible.

6.1.2 ADMINISTRATION AND/OR DOSING

Practice facilitation comprises on-site visits by the facilitator to meet with providers and/or staff. The schedule of visits is tailored to the practice but generally visits occur twice in the first month (to make a practice assessment) and then weekly to monthly thereafter (to effect practice change, provide education etc), with the goal of practice providers and staff working together to enhance their ability to deliver on-time HPV vaccination and encouraging persistence in the change process. Additional support via telephone and/or email will be available. Our own experience and reports in the literature^{31, 63} support the need for an extended time period for the change process to occur, with multiple PDSA

cycles. Practices will need time to expand their clinical focus to a population-based approach to identify and vaccinate eligible preteens who do not attend for a check-up visit.³¹ Strategies to identify and recall these patients will be new for many practices and include software, EMR features and staff outreach. In addition, completion of the vaccine series requires 6 to 12 months. Thus, practices will have access to the practice facilitator and intervention components for 2 years, including two “well-child” seasons, a time when providers in the pilot study reported it was easier to access the target age group and experiment with changes to HPV vaccine delivery.

Table 2. Roll-out of the intervention

Month 1	
Visit	Activities
Visit 1 Led by: Practice Facilitator and Principal Investigator and/or Project Coordinator (30-45 mins)	
 ▪ Review project goals ▪ Identify overall practice goals ▪ Introduce intervention components ▪ Introduce practice facilitator and review facilitation process ▪ Identify potential members for practice QI team ▪ Introduce practice assessment process
Practice Assessment with practice providers, practice manager, and/or staff involved in vaccine process Led by: Practice Facilitator	
 ▪ Understand provider and practice processes for giving HPV vaccine ▪ Understand practice workflow ▪ Learn individual provider goals for project ▪ Ask providers to participate in education by watching video
Visit 2 Led by: Practice Facilitator (30-45 mins)	
 ▪ Review baseline HPV vaccination rates for practice/U.S. ▪ Synthesize current HPV vaccination practices, provider individual project goals, and practice goals ▪ Discuss potential opportunities for improvement ▪ Establish practice goals for initiation and completion ▪ Decide focus for initial change idea targeting initiation ▪ Identify resources needed to accommodate change

Month 2	
Visit 3 Led by: Practice Facilitator (30-45 mins) (no more than 2-3 weeks after Visit 2)
 
 ▪ Determine first PDSA cycle to accomplish change idea ▪ Identify process needed to accommodate change ▪ Identify resources needed to accommodate change ▪ Decide how to monitor change
Month 3 – 2 Years	
Subsequent visits during change process Bi-weekly/monthly visits for 2 years (15-45 mins)
 
 ▪ Review success with PDSA cycle(s) and determine next steps ▪ Review considerations to implement change ideas ▪ Determine process for implementing change ideas and PDSA cycles ▪ Support practice QI team and efforts to make changes ▪ Provide education and skills training for providers and staff such as communication strategy, HPV vaccine, parental talking points, etc. ▪ Assist with self-monitoring of HPV vaccination to assess progress ▪ Assist with measurement for PDSA cycles ▪ Provide social support ▪ Share other primary care practices' best practices and change ideas ▪ Provide education for providers and staff about QI methods
Subsequent visits for Maintenance Led by: Practice Facilitator (check in every 2 weeks to monthly for 3 months)	
 ▪ Continue monitoring practice to check for sustainability ▪ Work with practice to trouble shoot any changes or procedures as needed ▪ Make sure the practice has access to all resources and tools as needed ▪ Provide process for obtaining MOC-Part 4 credits

6.2 FIDELITY

6.2.1 INTERVENTIONIST TRAINING AND TRACKING

[name] is responsible for training the practice facilitators, and for their supervision throughout the study period. Training is based on the AHRQ Practice Facilitator training and modules, accepted by the University of Buffalo Practice Facilitation Program.

Fidelity criteria were developed by the study team based on a literature review, best practices for facilitation^{71,72} and our experiences using facilitation in the pilot study. Every 12-months, use of the core components will be assessed and recorded by [name] using a 23-item observational measure (Table 3). All items will be scored on a 2-point scale (yes/no) or a percentage basis.⁷³ We will also track the time to achievement of key implementation milestones by noting dates of completion of specific activities (such as completion of provider education).⁷⁴ The facilitators will record the number and duration of visits to the practice, number of QI team meetings and attendees, and PDSA cycles undertaken. To supplement these measures, guide the intervention and assess the intensity of the facilitation process, the facilitator will keep detailed field notes about practice observations and interactions that will be reviewed with [name] at weekly meetings.

Table 3. Fidelity Score

HPV Vaccine Project Fidelity Score	Adherence		Dose	
Audit and Feedback	Yes	No		
Baseline data summary report is available				
Facilitator provides practice data and de-identified provider-level data to the QI team.			QI team reviews practice baseline data.	Y/N
Facilitator provides identified individual data to each provider			Providers who review own baseline data.	%
Facilitator encourages reflection and critical assessment of current practice and identification of performance gap(s).				
Provider/Staff education	Yes	No		
Facilitator reviews guideline recommendation for "on time" HPV vaccine with QI team.			Providers participate in education/training about "on-time" HPV vaccination (video, other).	%
Facilitator reviews rationale for age target with QI team.				
Facilitator provides educational resources to practices including guideline recommendations, videos, manuscripts.			HPV vaccine training provided to staff.	Y/N

Communication Strategy	Yes	No		
Facilitator educates providers and staff about the four key elements of the communication strategy.			Providers and key staff receive education re 4 key elements.	P= % S= %
Facilitator provides communication training opportunities for providers and staff.			Providers and key staff participate in communication strategy training.	P= % X RN & X PM
			Number of PDSA cycles targeting communication strategy.	#
Practice Facilitator to support using QI methods to effect change	Yes	No		
Facilitator meets individually with providers and practice manager.			Providers who meet with PF for baseline assessment.	%
			Meet with practice manager and/or staff for baseline assessment.	Y/N
Facilitator completes flow diagram summarizing current care, integrating baseline assessment and chart review data.				
Facilitator presents flow diagram summary to QI team.			QI team members who review flow diagram summary.	%
Core QI team comprises providers and staff.			Providers on initial QI team.	%

HPV Vaccine Project Fidelity Score	Adherence		Dose
	Yes	No	
PF to support using QI methods to effect change (cont.)			
Additional staff included as needed			QI team members who remain on team for 1 year. %
Number of QI team meetings in year 1 (count in-person visits, virtual meetings).			Total time spent (hours) in QI team meetings for providers, staff, and PF. P= S= PF=
Number of additional PF contact with practice/year.			
QI team address at least 2 change ideas per year to meet their targets for 'on time' delivery of HPV vaccine.			Number of changes accomplished for initiation and completion (determined by QI team). I= C=
QI team identifies metrics to monitor.			Number of completed measurement reviews of HPV vaccine use/year.
QI team implements system to monitor.			

Practice Facilitator

Quality of delivery: score 1 (poor) to 10 (excellent)	Score
PF ability to identify, assess, and summarize relevant data - consider baseline assessment, PDSA cycle measures and on-going monitoring	
PF ability to communicate effectively with QI team	
PF ability to encourage interactive problem solving and consensus building	
PF ability to encourage a diverse QI team including key personnel	

PF ability to encourage and sustain change efforts eg, shares info across practices, celebrates etc.	
PF ability to tailor facilitation activities to practice needs and circumstances	

Overall

Quality of delivery: score 1 (poor) to 10 (excellent)	Score
PF ability to identify, assess, and summarize relevant data - consider baseline assessment, PDSA cycle measures and on-going monitoring	
PF ability to communicate effectively with QI team	
PF ability to encourage interactive problem solving and consensus building	
PF ability to encourage a diverse QI team including key personnel	
PF ability to encourage and sustain change efforts eg, shares info across practices, celebrates etc.	
PF ability to tailor facilitation activities to practice needs and circumstances	

6.3 MEASURES TO MINIMIZE BIAS: RANDOMIZATION AND BLINDING

Bias: Although most providers will be from St Louis metropolitan area, they will be drawn from the bi-state area. We will gather information to describe participants and eligible non-participants to assess selection bias and allow others to assess the relevance of our findings to their situation.

Randomization: We will stratify practices into 2-groups by the number of providers. (≤ 4 and ≥ 5) We will randomize within the strata using a block design.

Blinding: It is not possible to blind investigators or practices from group assignment. The RA and the data analyst will be blinded to group assignment and are responsible for assessment of the primary and secondary outcome measures of HPV vaccine use. Blinding is not necessary for baseline measurements as this will occur prior to randomization. Thus, baseline measures may be completed by other members of the study team. In addition, measurement bias will be minimized for the assessment of these outcomes by using a standardized approach for data collection and analysis, as well as quality checks.

6.4 STUDY INTERVENTION/EXPERIMENTAL MANIPULATION ADHERENCE

The facilitators will record the number and duration of visits to the practice, number of QI team meetings and attendees, and PDSA cycles undertaken.

To supplement these measures, guide the intervention and assess the intensity of the facilitation process, the facilitator will keep detailed field notes about practice observations and interactions that will be reviewed at weekly meetings.

7 STUDY INTERVENTION/EXPERIMENTAL MANIPULATION DISCONTINUATION AND PARTICIPANT DISCONTINUATION/WITHDRAWAL

7.1 DISCONTINUATION OF STUDY INTERVENTION/EXPERIMENTAL MANIPULATION

If new knowledge becomes available regarding the safety or efficacy of the HPV vaccine use, the study may be discontinued.

7.2 PARTICIPANT DISCONTINUATION/WITHDRAWAL FROM THE STUDY

At the discretion of the PI, study participants may be withdrawn for noncompliance. Providers are free to withdraw from participating in the study at any time upon request. Parent/caregiver participation is one-time only with no follow-up and is limited to completion of one questionnaire.

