4.4 END-OF-STUDY DEFINITION

Intervention practices are considered to have completed the study after the baseline, 12-, 24- and 36-month measurements for vaccine coverage have been collected. Control practices may continue for an additional 24 months to receive the intervention.

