8 STUDY ASSESSMENTS AND PROCEDURES

8.1 ENDPOINT AND OTHER NON-SAFETY ASSESSMENTS

Mixed methods of data collection will be used including audit of the electronic medical record (EMR) to extract routinely collected and previously recorded data, surveys, and field notes. The study team will follow the same measurement procedures for both study groups.

The primary and secondary outcomes (vaccine initiation and completion by age 13, respectively) will be assessed by audit of the EMR, completed by the research assistant (RA) and/or a member of the study team. To assess variation among providers in the same practice, we will sample records from each participating provider. Measurement will be completed over four 12-month time periods (baseline, 12, 24, and 36 months). For each measurement period, the physician's office will provide an electronic list of eligible patients with an office visit with each participating provider. For each practice, a member of the study team will randomly select a sample of 60 records per provider from this list for review by the RA and or other member of the study team. As much as possible the number of records will be balanced across providers. Data abstracted from the record will include date and type of index visit (well child, acute care, and other e.g., immunization), date of birth, date of vaccination for HPV vaccine, Tdap, and MCV, sex, race/ethnicity and insurance status. Records will be de-identified for patient, provider and practice identifiers, and given a unique subject ID number.

Providers: At baseline and at 12- and 24-months, in addition to the EMR audit described above, all participating providers will complete a brief survey to assess their knowledge, attitudes and behaviors regarding HPV vaccination. The baseline survey will also assess demographic and other practices and physician-level factors that may affect intervention success and are needed to describe the study sample. The practice facilitator will keep detailed field notes about practice observations, contextual factors and practice change components, and will monitor the implementation process.

Practices: At baseline, the project coordinator and/or a member of the study team will meet with the practice manager to complete a brief practice survey to describe the practice and current HPV vaccination procedures. HPV vaccination procedures will be reassessed in a similar manner at 12- and 24- months.

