9.3 POPULATIONS FOR ANALYSES

Data analyses will adhere to the intention-to-treat principle, allowing 12-months grace period to implement practice changes. The primary analysis will compare the overall proportion of eligible preteens who initiated and completed HPV vaccination in the intervention and control practices at 24 months, using Year 2 measurements for vaccine use. Maintenance of change will be assessed using Year 3 measurements.

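### Does the plan leave it open whether patients of withdrawn providers stay in the outcome samples?

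*Combined protocol and SAP*

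**What the plan says.** Section 7.2 gives two routes out of the study: "At the discretion of the PI, study participants may be withdrawn for noncompliance", and "Providers are free to withdraw from participating in the study at any time upon request". Noncompliance is not defined. Section 7.3 (lost to follow-up) is marked not applicable.

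Section 8.1 describes the outcome sample. For each of the four 12-month periods the physician's office "will provide an electronic list of eligible patients with an office visit with each participating provider", and 60 records per provider are drawn at random. The section does not say whether participation is fixed at randomisation or judged again each period.

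On analysis, Section 9.3 states: "Data analyses will adhere to the intention-to-treat principle". Sections 9.4.1 and 9.4.2 repeat this, and 9.3 and 9.4.2 frame the primary comparison as one between preteens in intervention and control practices. Section 4.1 says vaccine use is assessed by practice, and Section 4.2 says by clinic. Section 1.3 lists the EMR review as a practice activity at baseline, 12, 24 and 36 months. Section 4.4 adds: "Intervention practices are considered to have completed the study after the baseline" and the three later coverage measurements are in hand.

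**The concern.** A provider who has withdrawn from participating is, in ordinary English, no longer a participating provider. On that reading a withdrawal under 7.2 also removes the provider's patients from every later sample. Section 6.3 says "It is not possible to blind investigators or practices from group assignment", so the PI would decide on noncompliance knowing the arm. Only intervention practices receive facilitation during the evaluation, so there may be more to be noncompliant with in that arm.

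The plan also places nearly all its clustering at the provider level (variance 0.75² against 0.01 for practices, Section 9.2). If the providers who left had unusual coverage, and left mainly from one arm, the comparison would no longer be of the groups as randomised. The intention-to-treat sentences govern how sampled records are analysed and do not say whose records are sampled. The imputation text in 9.4.2 does not deal with providers who are never sampled.

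**Working it through.** **What the term can mean.** There are three candidate readings.

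1. *Active in study tasks at the time.* Section 5.5 comes near this where it says that, for certification credit, "the pediatrician must participate in the intervention for at least 12-months". But that describes taking part in the intervention, not a sampling frame. It also fails for 8.1. The intervention lasts two years, and Section 1.3 schedules nothing for providers at 36 months. Under this reading no provider would be participating then, and the planned 36-month sample would be empty.
2. *Enrolled.* Section 5.5 uses the word this way: "We estimate that 27% of participating physicians will be male" describes the recruited group. This reading fits intention-to-treat, practice-level measurement and Section 4.4.
3. *Enrolled and not formally withdrawn.* No sentence rules this out. The real gap lies between readings 2 and 3.

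The N/A in 7.3 does not favour reading 3. Section 9.2 describes a cross-sectional design with patients as the unit of measurement, so no patient cohort is followed and the entry has an innocent explanation.

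**The plan's power figure.** Section 9.2 states power over 0.80 for 10 practices per arm, 4 providers each, 30 children each, 0.40 against 0.53, two-sided 0.05. The latent ICC is 0.5625/(0.5625 + 3.29) = 0.146, matching the stated 0.15. Simulation gives 0.87 if the two rates are population averages and 0.76 if they are set at a random effect of zero. A rough check with design effect 1 + 29 × 0.15 = 5.35 gives 0.79. The stated figure is reproduced under the first of these. It does not decide the present question.

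**Size under reading 3.** Inputs from the plan are coverage 0.40, provider SD 0.75 on the logit scale, 95 providers (47.5, taken as 48, per arm) and 60 records each. The number lost and the correlation between withdrawal and low coverage are assumptions, because the documents give neither.

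- An intercept of -0.456 gives mean coverage 0.40. The SD of provider coverage is then 0.1615 and the mean within-provider variance 0.2139.
- SE of the difference = √[2 × (0.1615² + 0.2139/60)/48] = √[2 × 0.02965/48] = 0.035, or 3.5 points.
- If k of 48 leave one arm, that arm's mean moves by k/(48 − k) × (arm mean − mean of those lost).

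Simulated shift in points when low-coverage providers leave one arm only:

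| Correlation | 1 lost | 2 lost | 5 lost |
|---|---|---|---|
| 0 | 0 | 0 | 0 |
| 0.3 | 0.22 | 0.41 | 0.92 |
| 0.5 | 0.35 | 0.66 | 1.50 |
| 1 (bound) | 0.62 | 1.19 | 2.83 |

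The shift is upward if they leave the intervention arm and downward if they leave control. Both signs reverse if high-coverage providers leave (about -0.95 and -1.61 points for 5 lost from the intervention arm). To read the table: 0.92 points with 5 lost means those five averaged 0.92 × 43/5 = 7.9 points below their arm. At correlations of 0.3 to 0.5 the shifts run from 0.22/3.5 = 0.06 to 1.50/3.5 = 0.43 standard errors. Losing one whole practice of ten in one arm gives 0.38 to 0.62 points at the same correlations.

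**Error rates** (t-test on provider proportions, practice variance ignored, so not the planned model). With 5 lost from one arm the null rejection rate is 0.058 or 0.073 at correlations 0.3 and 0.5, against 0.050 with none lost. With a true 13-point effect and 5 lost from control, power falls from about 0.95 to 0.90 or 0.87. Losing the same five at zero correlation already takes it to about 0.93, so part of the fall reflects fewer providers and not bias.

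**The case for a change.** The strongest case for acting is that the text never settles the matter. Section 8.1 itself requires all participating providers to complete surveys at baseline, 12 and 24 months. That cannot bind someone who has withdrawn, so the same phrase in the same section seems to exclude leavers. Heavier losses would also matter more. With 20% of intervention providers lost, none from control, and a correlation of 0.6, a simulation with a provider random-intercept logistic model gives a bias of 3.3 points and a null rejection rate of 0.19, against 0.07 with no withdrawal (Monte Carlo error 0.01 to 0.02). A sentence or two would close the gap, and practices are already paid yearly for lists and record access.

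What stands is that no sentence says whether a formally withdrawn provider's patients are still sampled. The survey wording is suggestive only, since it sets a task for providers and does not define the record frame, which the plan runs through the practice. The heavy-loss scenario needs a withdrawal rate, a one-sided pattern and a strong link to coverage, and the documents support none of the three. A sentence fixing the roster at randomisation would also leave open how to treat providers who join later, so it would not settle the frame.

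**Conclusion.** This is an undefined term that analysts following the plan would most likely resolve sensibly, by continuing to sample enrolled providers through their practices and analysing them as randomised. That reading agrees with the intention-to-treat statements, practice-level measurement, Section 4.4 and the 36-month schedule. A clarifying line would be harmless, but the plan does not need it.

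If the literal reading were applied, losing 1 to 5 of 48 providers from one arm would shift the difference by about 0.2 to 1.5 points at assumed correlations of 0.3 to 0.5, under half a standard error and small against 13 points. The shift is zero if withdrawal is unrelated to coverage, and it cancels if withdrawal follows the same pattern in both arms. The judgement rests on withdrawals being few or not strongly selective by arm, which the documents neither show nor contradict.
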